Use of a Red-Rubber Catheter to Facilitate Nasotracheal Intubation in Adult Patients: A Prospective Randomized Controlled Trial

NCT number: NCT03779984

Protocol Date: 02/14/2022

English ICF date: 05/09/2022

**The University of Texas Southwestern Medical Center at Dallas
Institutional Review Board**

Protocol

Use of a Red-Rubber Catheter to Facilitate Nasotracheal Intubation in Adult Patients: A Prospective Randomized Controlled Trial

Institution/Funding Source: Department of Anesthesia and Pain Management – University of Texas Southwestern Medical Center

1. Introduction and Purpose:

Nasotracheal intubation is used to facilitate oropharyngeal surgery in many patients, however, epistaxis is a common complication (1). Several methods to reduce epistaxis during nasotracheal intubation have been studied in adults and children. The use of a red-rubber catheter is effective in guiding nasotracheal intubation in children, however it has not been studied in adults in a prospective, randomized, controlled trial. This study was designed to compare the effectiveness of using a red-rubber catheter versus standard, direct insertion of a thermosoftened, lubricated nasal endotracheal tube into the naris to facilitate nasotracheal intubation in adults undergoing ENT, plastics or OMFS surgery. This study will assess if the red-rubber catheter method leads to lower incidence and severity of epistaxis, and faster time to intubation compared to the current standard of care.

Hypothesis 1 – The red-rubber catheter group will have significantly lower incidence of epistaxis compared to the standard insertion group in patients undergoing nasotracheal intubation.

Primary objective: To compare the incidence of bleeding after nasotracheal intubation.

Hypothesis 2 – The red-rubber catheter group will have significantly lower severity of epistaxis compared to the standard insertion group in patients undergoing nasotracheal intubation.

Secondary objective 1: To compare the severity of epistaxis after nasotracheal intubation.

Hypothesis 3 – The red-rubber catheter group will have significantly fewer airway complications compared to the standard insertion group in patients undergoing nasotracheal intubation.

Secondary objective 2: To compare the rate of complications during nasotracheal intubation.

Hypothesis 4 – The red-rubber catheter group will have significantly lower time to intubation than the standard insertion group.

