The study population for this prospective randomized controlled trial will consist of male and female adult subjects over the age of 18 having surgery requiring NTI. Consent will be obtained by study personnel. Eligible patients will be screened by study personnel up to 1 week prior to scheduled surgery. Informed consent will be obtained in the preoperative holding area. This is a multicenter study. The MD Anderson Center is other site of the study. Each study site will enroll 56 subjects. A total of 112 subjects will be randomized to either the RRC group or control group. Oxymetazoline nasal spray will be administered with 1 spray per nostril preoperatively. Premedication with glycopyrrolate 0.2 mg and benzodiazepine at discretion of provider will be given preoperatively. Subjects will then be brought into the operating room and placed on all standard ASA monitors (BP cuff, EKG, pulse oximetry). One spray of oxymetazoline per nostril will again be administered. Standard preoxygenation will be used with a face mask and 100% O₂. After induction of anesthesia, provider will confirm mask ventilation and 1 more spray of oxymetazoline will be administered per nostril. Intubation will first be attempted via a naris (13). Size 6.5 nasotracheal RAE tubes (Shiley Nasal RAE Tracheal Tube with TaperGuard Cuff, manufactured by Covidien llc, Mansfield, MA 02048) will be used in female patients and size 7.5 in males (16). The tubes will be thermosoftened by allowing them to sit in warm saline prior to use (18). Water-based lubrication will be used for dilation and intubation. Time from insertion of RRC or NETT into nasal passage to first recording of end-tidal CO₂ will be recorded. Direct video laryngoscopy will be used to facilitate placement of the nasotracheal RAE tube. Five minutes after intubation, a non-collaborating anesthesia provider blinded to the method of intubation will grade the severity of bleeding by performing direct video laryngoscopy, inspecting the posterior pharynx and using a scale described originally by Sugiyama et al (19) and again by Earle et. al (20)- no epistaxis (no blood observed on either the surface of the tube or the posterior pharyngeal wall); mild epistaxis (blood apparent on the surface of the tube or posterior pharyngeal wall); moderate epistaxis (pooling of blood on the posterior pharyngeal wall); and severe epistaxis (a large amount of blood in the pharynx impeding nasotracheal intubation—before the epistaxis assessor enters the

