Assuming the incidence of bleeding to be 50% and 24% in the control and RRC group, respectively, a sample size of 53 subjects per group (total n=106) are needed. This study is designed to have 80% power with alpha = 5%, two-sided. Assuming a dropout of 5%, a total of 112 subjects (56 in each arm) are required for this study. The sample size calculation was based on the chisquare tests.

Baseline characteristics (Demographics, Comorbidities) of all randomized patients will be summarized and presented in tables. Categorical variables will be presented as proportions and continuous variables as mean (SD) or median (range) as appropriate. The baseline differences between the two treatment arms will be assessed by Chi square/Fisher exact tests for proportions and Student t-test/Wilcoxon ranksum test for continuous variables as appropriate.

An intention to treat analysis will be conducted to assess the primary endpoint of bleeding. Logistic regression analysis will be conducted to model the primary endpoint between the treatment groups accounting for other confounders. Individual logistic regressions analyses will be conducted to model the secondary outcomes adjusting for treatment groups and other confounders. A univariate and a multivariable linear regression analysis will be conducted for those secondary outcomes, which are measured as continuous variables. A per protocol analysis will also be conducted where

patients with protocol violations will be excluded from the analysis. All analyses will be done using SAS 9.4 and $p < 0.05$ will be considered statistically significant.

15. References:

1. Chauhan, V. and Acharya, G. (2016) Nasal Intubation: A Comprehensive Review. *Indian Journal of Critical Care Medicine*, 20,662-667. doi:10.4103/0972-5229.194013
2. Hall, C.E. and Shutt, L.E. (2003) Nasotracheal Intubation for Head and Neck Surgery. *Anaesthesia*, 58, 249-256. doi:10.1046/j.1365-2044.2003.03034.x
4. Prasanna, D. and Bhat, S. (2014) Nasotracheal intubation: an overview. *Journal of Maxillofacial and Oral Surgery*, 13, 366-372. doi:10.1007/s12663-013-0516-5

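### Do the unstated time scale and the unstated form of the severity model weaken the two secondary analyses?

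*Combined protocol and SAP*

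**What the plan says.** Section 15 covers all secondary outcomes in two general sentences. The first reads "Individual logistic regressions analyses will be conducted to model the secondary outcomes adjusting for treatment groups and other confounders". The second reads "A univariate and a multivariable linear regression analysis will be conducted for those secondary outcomes, which are measured as continuous variables". Neither assigns a model to a named outcome. The option of "Student t-test/Wilcoxon ranksum test for continuous variables as appropriate" appears only in the paragraph on baseline differences.

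Two outcomes are at issue, both in section 1.

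- **Severity.** "Secondary objective 1: To compare the severity of epistaxis after nasotracheal intubation". Section 3 grades it as none, mild, moderate or severe, for example "moderate epistaxis (pooling of blood on the posterior pharyngeal wall".
- **Time.** Hypothesis 4 states that "The red-rubber catheter group will have significantly lower time to intubation than the standard insertion group". Section 3 measures "Time from insertion of RRC or NETT into nasal passage to first recording of end-tidal" CO₂, and its list of outcome measures counts from the first insertion.

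**The concern.** A clock that starts at first insertion and stops at first end-tidal CO₂ appears to include repeat attempts, a change of naris and rescue. Such times are usually right-skewed, and a comparison of mean seconds is then less sensitive to a proportional delay than one on the log scale. The delay matters: both paediatric trials of the catheter described in section 2 found it slower, against Hypothesis 4, so time is the likely price of less bleeding.

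For severity, the word logistic leaves the choice open. A none-versus-any split is the primary endpoint again, and a moderate-or-worse split ignores part of the scale. A proportional-odds model uses all four grades. If both changes were cheap and clearly better, leaving them out would cost two stated hypotheses some power and leave the choice of model until after the data are seen.

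**Working it through.** **1. The plan's own figure.** Inputs from section 15: 50% v 24% bleeding, 80% power, two-sided 5%, chi-square test. The mean proportion is 0.37.

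n = [1.960·√(2·0.37·0.63) + 0.842·√(0.50·0.50 + 0.24·0.76)]² / 0.26² = (1.338 + 0.553)² / 0.0676 ≈ 52.9, so 53 per arm.

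53/0.95 = 55.8, so 56 per arm and 112 in total. This matches the plan. Both outcomes in question are secondary, so no choice of model changes this number.

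**2. Is linear regression on seconds valid?** Simulated rejection under no difference, 53 per arm:

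- lognormal times, log-SD 0.3 to 1.0: 4.3% to 5.1%;
- adjusted model with 0, 2 or 5% very long cases in both arms: 4.1% to 5.2%.

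The test holds its level, and the mean difference in seconds is a legitimate quantity to estimate.

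**3. Seconds against log time.** The documents give no median, SD or rate of long cases, so these are assumed. Power at 53 per arm, two-sided 5%:

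| Assumed truth | Seconds | Log |
|---|---|---|
| Lognormal, 1.2-fold delay, log-SD 0.4/0.6/0.8 | 61/29/17% | 64/33/22% |
| Lognormal, 60 v 84 s, log-SD 0.4/0.6/0.8 | 98/73/45% | 99/81/57% |
| As above, 2% of cases 180 to 420 s longer in both arms | 70/55/38% | 95/75/53% |
| Normal, CV 0.35, 1.2-fold delay | 76% | 58 to 60% |
| Normal, CV 0.25, 1.2-fold delay | 96% | 92% |

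The normal rows keep the CV equal across arms. With equal SDs and CV 0.20 to 0.30, log loses only about 1 to 2.5 points.

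The large gain in the third row depends on 0.02 × 106 ≈ 2 very long cases, occurring equally often in both arms, in a population from which section 7 excludes difficult airways, abnormal nasal anatomy and BMI above 40. Section 2 reports that one paediatric trial needed fewer attempts with the catheter, so long cases may well differ by arm. The two scales then answer different questions. With equal true means and long cases at 10% in one arm and 2% in the other, log rejects 35% of the time and seconds 6%.

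**4. Severity when the odds are proportional.** The common odds ratio follows from the plan's rates: (0.24/0.76)/(0.50/0.50) = 0.316. The control grades (none/mild/moderate/severe) are assumed.

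| Control grades, % | Proportional odds | Any bleeding | Moderate or worse |
|---|---|---|---|
| 50/30/15/5 | 82% | 80% | 49% |
| 50/25/15/10 | 83% | 81% | 58% |
| 50/35/12/3 | 83% | 82% | 38% |

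Proportional odds gains 1 to 2 points over any bleeding, because none-versus-any is one of the cuts it pools and carries most of the information. It therefore does little to separate Hypothesis 2 from Hypothesis 1.

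**5. Severity when the odds are not proportional.** In children, section 2 reports less high-grade bleeding in one trial and less obvious bleeding in the other. Suppose incidence stays at 50% and moderate-or-worse falls from 20% to 8%. For the moderate-or-worse cut the mean proportion is 0.14:

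z = [0.12·√53 − 1.960·√(2·0.14·0.86)] / √(0.20·0.80 + 0.08·0.92) = (0.874 − 0.962)/0.483 = −0.18, so power is about 43%.

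| Assumed change | Proportional odds | Moderate or worse |
|---|---|---|
| Incidence unchanged, 20% to 8% | 9% | 43% |
| Incidence unchanged, 25% to 10% | 12% | 54% |
| Incidence 50% to 40%, 20% to 5% | about 33% | about 68% |

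In these cases the moderate-or-worse cut is the more sensitive analysis. If instead incidence falls from 50% to 24% with the same mix of grades among bleeders, the ordinal test has 77 to 79% against about 81% for any bleeding.

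**The case for a change.** The best case on the other side is about pre-specification, not power. Logistic regression on four grades can be binary at one of several cuts, multinomial or cumulative. Time can be analysed in seconds or on the log scale. These choices can give different answers to two stated hypotheses, and fixing them in advance removes discretion at no cost in patients. The moderate-or-worse cut does lose much power when the odds are proportional, and log time does gain when times are strongly skewed.

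It stands that the plan leaves this detail out, and that a sentence naming the scale and the severity model would make it clearer. Three things limit the point.

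- With no transformation named, linear regression reads most naturally as seconds, which is valid. If time is the trade-off, mean seconds with a confidence interval expresses it directly.
- The cumulative-logit model is itself a logistic regression, so the plan's wording already allows it.
- The case for these particular models depends on assumed skew and an assumed common odds ratio. The plan's own background points partly the other way: fewer attempts, and less high-grade bleeding.

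**Conclusion.** The concern does not hold. Section 15 is brief, but what it names is valid for both outcomes, and neither proposed model is better across plausible conditions. Without very long cases, log time gains 3 to 4 points for a 1.2-fold delay and 1 to 12 points for a 1.4-fold delay. It can lose 16 to 18 points if times are symmetric, and it changes the question if long cases differ by arm. Proportional odds gains 1 to 2 points over any bleeding, and has about 9% power against 43% for a moderate-or-worse cut if severity alone improves.

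These figures rest on assumed time distributions and grade splits at 53 per arm; only the odds ratio of 0.316 comes from the plan. Experienced statisticians could reasonably choose either way on both outcomes. The primary analysis, its type I error and the total of 112 do not depend on the choice.
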